Functional outcome will be measured using the modified Rankin Scale (mRS)¹⁶ as well as the Lawton Instrumental Activities of Daily Life Scale (IADL)¹⁷ three and twelve months after the index event.

Second secondary hypothesis:

Ischemic stroke patients with a dynamic change of troponin values have poorer cognitive outcome than patients with stable troponin values three and twelve months after the index event.

Endpoint:

Cognitive outcome will be evaluated using the Montreal Cognitive Assessment (MoCA)¹⁸ and the Telephone Interview for Cognitive Status (TICS)¹⁹

Third secondary hypothesis:

Ischemic stroke patients with a dynamic change of troponin values have an increased risk of recurrent cardiovascular events and mortality compared to patients with stable troponin values.

Endpoint:

Rates of recurrent ischemic strokes, TIA, myocardial infarction and mortality after three and twelve months.

Study population:

According to the sample size calculation, 251 stroke patients will be included prospectively. Both male and female patients will be included. Pregnant or breastfeeding patients will not be eligible for inclusion. The study will only recruit patients ≥ 18 years of age.

Inclusion criteria:

- age ≥ 18 years
- written informed consent
- diagnosis of ischemic stroke based on clinical symptoms and imaging (cranial CT or MRI) < 72 h after symptom onset
- troponin elevation:
 - a) either highly abnormal initial troponin levels (Elecsys-Assay hs-cTnT > 52 ng/l, Architect-Assay hs-cTnI > 52 ng/l²⁰, Dimension Vista Assay hs-cTnI > 107 ng/l²¹)
or
 - b) dynamic troponin elevation with Δ change $> 20\%$ of the initial value after 3 hours and at least one value above the assay-specific upper reference limit according to ESC guidelines¹²
- diagnosis of transient ischemic attack, if the initial focal neurological deficit was objectified by a neurologist during clinical examination and the patient has an ABCD2-Score²² ≥ 4 points
- patient willing to participate in follow-up via telephone interview

Exclusion criteria:

- renal insufficiency (i.e. estimated glomerular filtration rate (eGFR) < 30 ml/min/1,73 m²)²²
- manifest hyperthyroidism
- cerebral infarct > 100 ml on diffusion weighted imaging (DWI-MRI) or on cranial CT (if performed > 24 hours after symptom onset) or ASPECTS-Score²³ < 7 (if cranial CT was performed within 24 hours of symptom onset)
- pregnancy or breast feeding

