2.3 Sample size

To be assessed for eligibility (n = 8,750 patients with ischemic stroke, thereof n = 1,250 with troponin elevation according to the inclusion criteria)

To be allocated to trial (n = 251)

To be analyzed (n = 203)

Full details of sample size calculation can be found in the study protocol.

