4.5 Baseline patient characteristics

Baseline is defined as the measurement recorded at hospital admission (< 72 h after admission) (“V1”). All relevant characteristics to be measured at baseline are listed in table 1 of the study protocol (Nolte, et al. 2020)). Patients will be described with respect to

- Age
- Gender
- Medical history/comorbidities
 - o Diabetes mellitus
 - o Hypertension
 - o Hyperlipidemia
 - o History of coronary artery disease
 - o Heart failure
 - o Atrial fibrillation
 - o Previous history of stroke
 - o history of cancer
 - o smoking status
- acute therapy of ischemic stroke
 - o i.v. thrombolysis
 - o thrombectomy
- Physical examination
 - o Heart rate on admission
 - o systolic blood pressure on admission
 - o diastolic blood pressure on admission
- Current Medication
 - o Antiplatelet therapy
 - o dual antiplatelet therapy
 - o oral anticoagulation
 - o statin
 - o beta-blockers
- NIHSS
- mRS
- GRACE Score
- MoCA
- Creatinine
- Haemoglobin
- Peak troponin T

both overall and separately for presence/absence of dynamic troponin elevation and additionally for the presence/absence of ACS as well as for the diagnostic categories no ACS, MI Type 1 and MI type 2. Categorical data will be summarised by numbers and percentages. Continuous data will be summarised by mean, SD, median, IQR and range. Number of available observations and number of missing observations will be presented for the diagnostic groups (dynamic vs. stable) separately and overall for both groups. Differences in baseline variables between the two diagnostic groups will be analysed by appropriate tests, e.g. Chi-squared test, Mann-Whitney-U test, or analyses of variance.

5 Analysis

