5.3.2 Adjusted analyses

For the primary endpoint univariate and multiple logistic regression models will be fitted to the data to calculate unadjusted and adjusted odds ratios, including a series of baseline regressors:

- Age (continuous)
- Gender (dichotomous)
- Diabetes (dichotomous)
- Dyslipidemia (dichotomous)
- Renal failure (eGFR < 60 ml/min dichotomous)
- History of CHD (dichotomous)
- History of heart failure (dichotomous)
- History of atrial fibrillation/flutter (dichotomous)
- Haemoglobin (<12 g/dl for women, < 13 g/dl for men, dichotomous)
- Initial NIHSS (continuous)
- Heart rate (> 100/min, dichotomous)
- ECHO core lab: wall motion disturbance (dichotomous)
- ECG core lab findings: ACS typical changes (dichotomous)
- Peak troponin T value (continuous)

In an explorative analysis, an optimized multiple logistic regression model for the prediction of the primary endpoint is derived using the following procedure: in the first step, a multiple logistic regression model is established in a blinded manner, i.e. without taking troponin values into account, including relevant confounding variables into the model. In order to decide which variables are included in the model, clinical and statistical criteria are used, considering the distribution of the variables and their structure of missing values.

In the second step, variable selection is performed using backward selection.

In the last step, an unblinded analysis is performed, i.e. the troponin is included in the prognosis model to predict the primary endpoint. The final choice of variable selection method is based on the technical feasibility of the model, use of performance parameters, and clinical considerations. For the calculation of the ROC-AUC as performance measure, a 10-fold validation procedure will be performed.

The same procedure is applied in order to derive a prognostic model for the prediction of the presence of type 1 myocardial infarction as well as in those patients in whom ACS is present, for the prediction of type 1 vs. type 2 myocardial infarction as adjudicated by the EAC.

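### SAP 5.3.2 enters eGFR, haemoglobin and heart rate as yes/no regressors although the numeric values are available, which probably loses information and saves no parameters

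*SAP*

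**What the plan says.** SAP 5.3.2 states that for the primary endpoint "univariate and multiple logistic regression models will be fitted to the data to calculate unadjusted and adjusted odds ratios", and lists 14 baseline regressors with their coding. Three of them are measurements turned into categories:

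- "Renal failure (eGFR < 60 ml/min dichotomous"
- "Haemoglobin (<12 g/dl for women, < 13 g/dl for men, dichotomous"
- "Heart rate (> 100/min, dichotomous"

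The other numeric regressors are kept as numbers: age, peak troponin T and "Initial NIHSS (continuous".

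The underlying values exist. SAP 4.5 lists "Heart rate on admission", haemoglobin and creatinine among the baseline characteristics and says that continuous data will be summarised by mean, SD, median, IQR and range. eGFR is not named in 4.5, but the protocol's exclusion criteria use a numeric limit, "estimated glomerular filtration rate (eGFR) < 30 ml/min/1,73 m²", so a value should exist for each enrolled patient.

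The regressors named in the protocol's statistical section do not include these three variables, so it gives no reason for the cuts either. The eGFR cut of 60 is the one used for the subgroup analysis in SAP 5.3.1. No sensitivity analysis with continuous terms is planned.

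**The concern.** A dichotomy treats everyone on one side of the cut as identical. Among enrolled patients, an eGFR of 31 and one of 59 become the same value, while 59 and 61 become different ones. Two things follow if the true relation is graded. The covariate explains less of the outcome than it could. And if it is related to both troponin change and ACS, part of that confounding stays in the adjusted odds ratio.

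The usual excuse for a cut, that it saves parameters, does not apply against a linear term. The plan already accepts linear terms for the other three numeric covariates.

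At stake are the adjusted odds ratios in 5.3.2 and, if the coding is carried forward, the exploratory prediction model. There, a covariate weakened by cutting is more likely to be dropped by backward selection. SAP 5.3.3 then adjusts for the variables found in that step.

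**Working it through.** **1. Parameter count.** The list in 5.3.2 has 14 regressors, or 15 terms with dynamic troponin. Replacing three binary terms by three linear terms leaves 14 (15). The sex-specific haemoglobin limits need no extra term, because gender is already in the list.

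**2. Information kept by a cut.** The documents give no figure to reproduce here. For a normal covariate with a linear log-odds effect (assumptions), the share of information kept by a binary version with proportion p beyond the cut is approximately the squared correlation between the two versions:

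φ(z)² / [p(1 − p)], where z is the normal quantile at the cut and φ the normal density.

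| Share beyond cut, p | z | φ(z) | Information kept |
|---|---|---|---|
| 50% | 0 | 0.399 | 0.159 / 0.25 = 64% |
| 30% | 0.524 | 0.348 | 0.121 / 0.21 = 58% |
| 20% | 0.842 | 0.280 | 0.078 / 0.16 = 49% |
| 10% | 1.282 | 0.175 | 0.031 / 0.09 = 34% |
| 5% | 1.645 | 0.103 | 0.0106 / 0.0475 = 22% |

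The documents do not say what share of patients lies beyond each limit, so the whole range is shown.

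**3. What this means for one covariate.** Logistic regression was simulated with N = 203 (SAP 2.3: "To be analyzed (n = 203"), 24% events and an assumed odds ratio of 1.65 per SD. Power to detect the covariate was about 82–84% with a linear term. With a cut it was about 67% at 50/50, 61% at 30/70 and 46% at 10/90.

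**4. The mirror case.** The squared correlation is symmetric. If risk truly steps up at the cut, a linear term keeps the same 34% (10/90), 49% (20/80) or 58% (30/70), and the binary term is the efficient one. With a true step of odds ratio 3 (assumption) and the same N and event rate, simulated power was about 61% binary against 32% linear at 10/90, and 79% against 56% at 20/80, to within a few points of simulation error.

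**5. Events, for context.** The documents give no event count for this model. Two proxies, both based on coronary culprit lesions in the earlier study and not on adjudicated ACS:

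- Earlier study's overall rate: 203 × 7/29 = 49 events; 49/14 = 3.5 per listed regressor.
- Sample-size inputs: 6% in the stable group and odds ratio 4 give 20.3% in the dynamic group. With an 11:18 split, two-sided alpha 0.05, 80% power and a continuity correction, these inputs reproduce the protocol's 203 as 126 stable + 77 dynamic. Expected events are 126 × 0.06 + 77 × 0.203 ≈ 23; 23/14 ≈ 1.7 per regressor.

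At the planned inclusion of 251 the first rate gives about 61 events (4.3 per regressor). These ratios are the same under either coding, by step 1.

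**The case against.** The strongest reply is that the shape of each effect is unknown. The loss in step 2 holds only under linearity, and step 4 shows that a threshold reverses it. Normality is also doubtful for eGFR, since patients below 30 are excluded. Cut-points fixed in advance avoid data-driven choices of shape, are familiar to clinicians, and for eGFR match the planned subgroup. Flexible terms would not be free: two parameters for each of the three variables would take 15 terms to 18. All of this stands, and it is why the percentages are conditional. It does not explain why these three variables are treated differently from age, NIHSS and troponin, for which the plan accepts linearity.

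Three stronger readings are tempting, and the documents do not support them.

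- *That the prediction algorithm is built on dichotomised data.* The coded list belongs to the adjusted odds-ratio models. The paragraph on the optimised model does not restate the list or its codings, and selects variables on clinical and statistical criteria. Carry-over is plausible but not stated.
- *That the coding worsens the shortage of events.* It neither causes nor cures it. Events per parameter is a separate issue.
- *That the main result is at risk.* SAP 5.1.1 tests an unadjusted diagnostic odds ratio. The models in 5.3.2 are additional analyses, and the prediction model is labelled explorative.

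It is also fair to say that no effect on the adjusted troponin odds ratio or on the AUC has been quantified, and that nothing in the documents shows how strongly these three variables confound the troponin–ACS relation.

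**Conclusion.** The point holds as a minor, inexpensive improvement to a supporting analysis; it is not an error in the primary analysis. Three available measurements are cut without a stated reason and without saving a parameter, against the plan's own handling of its other numeric covariates. Under roughly normal covariates and roughly linear effects, the cut versions keep between about a third (10/90) and two thirds (50/50) of each covariate's information, and leave whatever confounding varies within each category. The size depends on the unknown shares beyond the cuts and on effect shape. The primary odds ratio and the sample size of 203 are untouched.

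**What to change.** In SAP 5.3.2, enter eGFR, haemoglobin (with gender in the model) and heart rate as continuous linear terms. Add a sentence that the same coding applies to these variables when they are candidates for the exploratory prediction model, so that the coding is settled before backward selection. Keep the eGFR 60 split for the subgroup analysis in 5.3.1, and keep all three cut-points for description and for a sensitivity analysis of the adjusted model. The sensitivity analysis also covers the case of a threshold effect.

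The cost is SAP wording only, with no new data and no extra parameters. The downside is that linearity is assumed for three more variables, and continuous terms are slightly less convenient at the bedside.

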In the general population, previous studies have found an association between higher troponin levels and poorer cognitive performance¹⁴. Higher troponin levels were especially associated with poorer executive function. Moreover, chronic heart failure is associated with cognitive decline¹⁵. This interaction between heart and brain has not been fully elucidated. In particular, it remains unclear whether a dynamic change of troponin levels is associated with poorer cognitive performance in patients with acute ischemic stroke.

Study aims:

The primary aim of the PRAISE study is to develop an algorithm for the prediction of acute coronary syndrome in acute ischemic stroke patients using non-invasive diagnostic tests. In order to improve prediction of acute coronary syndrome in patients with acute ischemic stroke, serial troponin measurements, ECG, echocardiography, GRACE score and clinical symptoms will be evaluated systematically and prospectively for the first time. Moreover, we aim to clarify whether a dynamic troponin elevation is associated with poor functional and cognitive outcome as well as higher mortality after stroke.

Setting:

The study is financed by the German Center for Cardiovascular Research (DZHK) and the German Center for Neurodegenerative Diseases (DZNE). About 15 stroke centers in Germany will participate as recruiting study sites. The majority of recruiting study sites are university hospitals with both a neurology and a cardiology department. The PRAISE study is an observational study. Therefore, treatment of patients included in the PRAISE study will be at the discretion of the local treating physicians.

Hypotheses:

The **primary hypothesis** states that a dynamic change of troponin values > 50% after 3 hours¹ indicates acute coronary syndrome in patients with acute ischemic stroke. In patients with acute ischemic stroke, change of troponin values in serial measurements is helpful to identify patients with acute coronary syndrome.

Endpoint: diagnosis of acute coronary syndrome as established by an independent endpoint adjudication committee.

First secondary hypothesis:

Ischemic stroke patients with a dynamic change of troponin values have poorer functional outcome than patients with stable troponin values after three and twelve months.

Endpoint:

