The decision on early termination of the study at an individual study site is made by the principal investigators after consulting the Steering Committee. If an individual study site wishes to terminate their participation prematurely, they are required to notify the principal investigators in writing.

Study procedures:

Patients with acute ischemic stroke that undergo inpatient treatment at one of the PRAISE study sites may be included into the PRAISE study. Acute ischemic stroke will have to be diagnosed by an experienced neurologist at the recruiting study site. All patients will undergo cranial imaging (i.e. cCT or cMRI) as part of clinical routine before inclusion to rule out differential diagnoses to ischemic stroke. Patients will be eligible for inclusion within 72 hours after hospital admission. ECG, echocardiography and coronary angiography will have to be performed within 7 days after hospital admission.

Patient history and clinical examination:

Upon study inclusion (V1) the patient's clinical history will be taken and a clinical examination will be performed. The data will be collected in accordance with the DZHK basic data set (DZHK-SOP-K-02)²⁵. In addition, we will gather data on current medication, premorbid mRS, the National Institutes of Health Stroke Scale (NIHSS)²⁶ on admission as well as the GRACE-Score. During the second study visit (V2, within 7 days after study inclusion), we will perform the NIHSS, mRS and perceived stress scale

(PSS). In addition, we will collect data on the patient's current medication. A 12-lead ECG will be taken at V1 and V2 according to DZHK-SOP-K-03²⁷.

Coronary angiography:

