All patients included in the study will undergo coronary angiography, which is the gold standard to diagnose a coronary culprit lesion. The timing of coronary angiography will be determined according to the ESC guideline recommendations on risk stratification²⁸. Coronary angiography will be performed according to a SOP. Treating cardiologists may choose the cardiac catheter for coronary angiography. We will collect data on duration of the procedure, amount of contrast agent given, puncture site (radial vs. femoral), periprocedural anticoagulation, balloon dilatation and stent angioplasty. In addition, we will collect data on periprocedural complications, e.g. dissections, arrhythmias, thrombus formation, perforation, cardiac tamponade and type 4a myocardial infarction. For central reading in the core laboratory, imaging data will be uploaded via the imaging data management system (BDMS) of the DZHK. Coronary lesions will be evaluated regarding their localization and morphology according to the AHA classification.

Echocardiography:

Transthoracic echocardiography (TTE) will be performed by a cardiologist at the participating study site according to DZHK-SOP-K-08²⁹. For central reading in the core laboratory, imaging data will be uploaded via the imaging data management system (BDMS) of the DZHK.

Troponin:

Acute ischemic stroke patients with elevation of troponin values according to the inclusion criteria (see above) will be eligible for inclusion into the PRAISE study. Troponin will be measured on admission and after three hours during clinical routine in all recruiting study sites. A dynamic elevation of troponin is defined as a 20% change of troponin values in serial measurement with at least one value elevated above the assay-specific upper reference limit. Since not all recruiting study sites will use the same assay for measuring troponin in clinical routine, troponin will also be measured at a central core laboratory located at the University Hospital Hamburg-Eppendorf ([name]). At the core laboratory, high-sensitivity (hs)-Troponin-T will be measured using the Roche Elecsys-Assay and hs-Troponin I will be measured using the Siemens Architect-Assay.

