Troponin (0 und 3 h)	X			
Clinical chemistry	X			
DZHK-Biobanking (optional)		X		
Study-specific examinations				
GRACE-Score	X			
Adverse Events	X	X	X	X
ECG	X	X		
Echocardiography (TTE)		X		
Coronary angiography		X		
endpoints				
Acute coronary syndrome (ACS)		X		
Recurrent cerebral ischemia, myocardial infarction, mortality		X	X	X

Table 1: PRAISE study procedures

Statistical analysis:

Sample size calculation:

The sample size calculation of the PRAISE study is based on data from the TRELAS study (Troponin elevation in acute stroke)⁹. In the TRELAS study, 7/29 (24%) of ischemic stroke patients with troponin elevation had a coronary culprit lesion and 11/29 (38%) of patients had dynamic troponin elevation (i.e. Δ change $> 50\%$). Of 11 patients with dynamic troponin elevation, 6 patients (54%) had a coronary culprit lesion. In patients without dynamic troponin elevation, only one patient (1/18=6%) had a coronary culprit lesion. Thus, the odds ratio of a dynamic troponin elevation for presence of a coronary culprit lesion was at 20.4. Due to the small sample size of the TRELAS study, we used the lower limit of the 80% confidence interval of the odds ratio (~4) to calculate the sample size for the PRAISE study. We assumed that the proportion of stroke patients with dynamic troponin elevation will be similar to the TRELAS study. Thus, 203 patients will have to be included to achieve a statistically significant result with a power of 80% (alpha=0.05). Since the TRELAS study only recruited patients with an initial hs-troponin T value > 50 ng/l (Roche Elecsys Assay), the proportion of patients with dynamic troponin elevation will likely be even higher in PRAISE. In order to compensate for cases of withdrawal of consent we plan to include 251 patients. The primary hypothesis will be tested using an intention-to-diagnose analysis by calculation of the odds ratio of acute coronary syndrome in patients with dynamic vs. stable troponin elevation. Secondary endpoints will be analyzed using the same statistical method.

In order to assess other predictors of acute coronary syndrome we will use the Chi-Square-test for dichotomous variables and the Wilcoxon-Test for continuous variables.

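### Wall motion enters the ACS models as a baseline regressor, but the only scheduled echocardiogram is at V2 and may follow angiography

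*SAP*

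**What the plan says.** SAP 5.3.2 plans univariable and multiple logistic models for ACS, "including a series of baseline regressors". One of the 14 regressors is "ECHO core lab: wall motion disturbance (dichotomous", and another is ACS-typical change on the core-lab ECG. Neither carries a time point. The protocol's Statistical analysis section also puts both findings among its baseline regressors.

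SAP 4.5 fixes the meaning of the term: "Baseline is defined as the measurement recorded at hospital admission (< 72 h after admission", which is V1.

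The protocol's Table 1 marks "Echocardiography (TTE" at V2 only, the visit at which coronary angiography is also marked. ECG is marked at V1 and V2. Under Study procedures the only timing rule is: "ECG, echocardiography and coronary angiography will have to be performed within 7 days after hospital admission". Under Coronary angiography: "The timing of coronary angiography will be determined according to the ESC guideline recommendations on risk stratification". The procedure data collected there include "periprocedural anticoagulation, balloon dilatation and stent angioplasty".

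The primary aim is to "develop an algorithm for the prediction of acute coronary syndrome in acute ischemic stroke patients using non-invasive diagnostic tests". The Background gives the reason: angiography is invasive, clinicians hesitate to use it after stroke, and patients with a high prior likelihood of a culprit lesion need to be identified.

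**The concern.** An algorithm that helps decide who goes to angiography can use only what is known before angiography. If a site performs angiography on day 2, treats a lesion, and records the echocardiogram on day 5, the plan accepts that echocardiogram as the wall-motion regressor. SAP 3.2 counts a missing echocardiogram as a minor deviation and says nothing about the order of the tests.

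A post-treatment finding may differ from the one the clinician would have seen. Wall motion may recover after revascularisation, or an abnormality may be caused by the procedure (the protocol collects type 4a infarction as a complication). Revascularisation would be expected mainly in patients with ACS, so any resulting shift would tend to differ by outcome. The regressor's odds ratio, the AUC and the weights in the algorithm could then describe a different setting from the one in which the algorithm is to be used. The 10-fold validation in SAP 5.3.2 would not reveal this, because every fold has the same mixture of timings.

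This is separate from the committee's use of ECG and echocardiography in adjudicating ACS. Resolving one would leave the other.

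**Working it through.** **Step 1: label against schedule.**

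| Regressor in SAP 5.3.2 | Scheduled (protocol Table 1) | Baseline under SAP 4.5 (V1)? |
|---|---|---|
| Core-lab ECG change | V1 and V2 | Yes, if the V1 recording is used |
| Core-lab wall motion | V2 only | No |

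No scheduled echocardiogram meets the SAP's own definition of baseline. This needs no assumption.

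**Step 2: order of tests.** Echocardiography and angiography share a visit and a 7-day limit. Angiography timing follows risk stratification and is not tied to the echocardiogram. Neither document requires the echocardiogram first, restricts the models to earlier recordings, or plans an analysis by test order.

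**Step 3: analyses reached.** The primary odds ratio (SAP 5.1.1) compares ACS between dynamic and stable troponin and uses neither echocardiography nor ECG as a predictor. The regressor enters the adjusted and optimised models (SAP 5.3.2) and the ROC analysis and algorithm (SAP 5.3.3).

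**Step 4: possible size.** The plan gives no figure to reproduce here, so every input is an assumption. Take a pre-angiography abnormality in 60% of ACS and 20% of non-ACS patients:

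OR = (0.60/0.40)/(0.20/0.80) = 6.0.

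Let f be the share of ACS patients scanned after angiography, v the share of those who were revascularised, and r the share of abnormalities that resolve after revascularisation. Then

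p = 0.60 × (1 − f·v·r), and OR = 4 × p/(1 − p).

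| f | v | r | p | OR |
|---|---|---|---|---|
| 0.25 | 1 | 0.2 | 0.570 | 5.3 |
| 0.25 | 1 | 0.3 | 0.555 | 5.0 |
| 0.50 | 1 | 0.3 | 0.510 | 4.2 |
| 0.75 | 1 | 0.3 | 0.465 | 3.5 |
| 0.50 | 0.5 | 0.3 | 0.555 | 5.0 |
| 0.50 | 1 | 0.5 | 0.450 | 3.3 |
| 1 | 1 | 0.2 | 0.480 | 3.7 |
| 1 | 1 | 0.5 | 0.300 | 1.7 |

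The other direction: if instead a share g of late-scanned ACS patients with normal wall motion acquire an abnormality, p = 0.60 + 0.40·f·g. This exceeds 0.60 for any g above zero, so the OR exceeds 6.0.

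**Step 5: what a restriction leaves.** In the earlier study used for planning, 7/29 (24%) had a culprit lesion. Taking that as the ACS rate, 203 × 7/29 = 49 patients. If 50% or 75% of echocardiograms are late, about 24 or 12 ACS patients keep a pre-angiography one.

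The rates behind the sample size imply fewer. A stable-group rate of 6% with an odds ratio of 4 gives 0.24/1.18 = 20.3% in the dynamic group. With a 11:18 split, two-sided 5% alpha, 80% power and continuity correction, the protocol's 203 is reproduced as 126 + 77. Expected ACS is then 126 × 0.06 + 77 × 0.203 = 23, leaving about 12 or 6.

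**The case against.** - **The ECG.** A reader might infer that a post-angiography ECG also feeds the models. The documents do not support that: baseline is V1, a V1 ECG exists, and the ECG is called a baseline regressor, so a consistent reading points to the V1 recording. Naming it is a clarification. A date check is still worthwhile, since V1 extends to 72 hours.
- **Certainty of harm.** A reader might infer that the algorithm's performance will be wrong, or that wall motion will look weaker than it is. Neither follows. Most echocardiograms may precede angiography, and recovery and procedural injury push in opposite directions. The angiography and echocardiography SOPs cited by the protocol are not among the documents and might set an order. The absence of any rule in the SAP stands regardless.
- **Size.** Most rows in Step 4 assume that every late-scanned ACS patient was revascularised. ACS here includes unstable angina (SAP 1.2.1) and type 2 infarction (SAP 5.3.2), and the protocol leaves treatment of confirmed ACS to case-by-case discussion. With half revascularised, the f = 0.50, r = 0.3 case moves from 4.2 back to 5.0. This objection stands.
- **The remedy can add bias.** Angiography timing follows risk, so discarding late echocardiograms may make missingness depend on risk and outcome, and Step 5 shows how thin the data could become against 14 regressors. This also stands, and is why deletion alone is not proposed.
- **Scope.** The optimised model and the rule-in/rule-out algorithm are labelled exploratory. That is so, but developing the algorithm is the stated primary goal in both documents.

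**Conclusion.** The concern holds as a gap in the SAP. The wall-motion regressor is called baseline when the only scheduled echocardiogram is not, and nothing in the two documents keeps post-angiography recordings out of the models. That much rests on the text alone. That the algorithm is for use before angiography is inferred from the protocol's Background and Study aims.

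The share of late echocardiograms, and the size and direction of any bias, are unknown. The odds ratios of 5.3 to 1.7 show what resolution of abnormalities could do under assumed inputs; they are not estimates for this study.

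A reader might infer that the primary result is compromised. It is not: SAP 5.1.1 uses neither test as a predictor, and the sample size is unchanged. The adjusted models, prediction models and algorithm in SAP 5.3.2 and 5.3.3 are at risk, so this should be corrected before those analyses are run.

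**What to change.** All changes are to the analysis; none alters the order in which sites perform the tests.

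1. State in SAP 5.3.2 that the ECG regressor is the V1 core-lab ECG, provided it was recorded before angiography.
2. Stop calling the V2 echocardiogram a baseline regressor, and derive from the procedure dates whether each one preceded angiography. The protocol's variable list does not show whether clock times are held. If only dates exist, treat same-day pairs as order unknown and show the results both ways.
3. Report the number of echocardiograms before and after angiography, by ACS status.
4. In SAP 5.3.2 and 5.3.3, report the prediction models and AUC with pre-angiography echocardiograms only, beside the any-time version. Treat later ones as missing and handle them with the SAP 5.2 multiple imputation. The imputation variables named there do not list wall motion, so it must be added, along with ACS status.
5. Base any claim about performance before angiography on the restricted version.

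The cost is SAP wording, use of procedure dates and one further set of models. The downside is fewer usable echocardiograms, possibly missing in relation to risk, and wider intervals if late ones are common. In that case the counts in item 3 would show how far the study can support an echocardiographic component at all.
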